5.1 Informed Consent Acquisition

5.1.1 Preparation of "Informed Consent Form" and "Explanatory Document"

The "Informed Consent Form" and "Explanatory Document" are prepared by the principal investigator and approved by the ethics committee.

5.1.2 Timing and Methods of Informed Consent Acquisition

When obtaining consent from the patient, the principal investigator or attending physician will first provide the patient with the "Explanatory Document" and explain the study purpose/methods, etc., in an understandable manner. Next, they address the patient's questions about the study to confirm that they have fully understood the study content. Finally, the patient's willingness to voluntarily participate in this clinical study based on free will will be confirmed, and this will be documented by the patient signing/sealing or initialing the dated "Informed Consent

Form".

When obtaining consent from the patient, the principal investigator or attending physician will confirm the patient's contact information and the contact information of the patient's family members or other emergency contacts, and record this in the medical records under the management of the participating institution.

5.1.3 Acquisition, Storage of "Informed Consent Form", and Case Registration

The principal investigator or attending physician who provided the explanation and the subject will each fill in the date, sign/seal or initial the "Informed Consent Form". The original copy will be stored by the principal investigator or the physician performing regenerative medicine, and a copy will be stored by the personal information manager after linkable anonymization. After obtaining consent, the principal investigator or attending physician will entrust the case registration center to register the case. In addition, before the subject participates in the study, a copy of the signed/sealed and dated informed consent form will be provided to the subject, and the date of delivery will be recorded.

5.1.4 Documentation of Informed Consent Acquisition Date

The principal investigator or the physician performing regenerative medicine will record the date of obtaining informed consent from the subject in the case report form.

6. Study Implementation Schedule

6.1 Pre-transplantation 1-7 days ~ Screening Period

6.1.1 Informed Consent Acquisition

The principal investigator or attending physician must obtain written informed consent from the patient and assign a subject identification code before performing any examinations/observations related to this clinical study. Informed consent must be obtained 1–2 days before surgery.

6.1.2 Eligibility Confirmation

Based on specified examinations/observations, the principal investigator and attending physician will confirm whether the candidate subject meets the inclusion criteria and does not violate the exclusion criteria (preliminary eligibility confirmation). Furthermore, based on the screening examination results, final eligibility confirmation will be performed within 1–2 days before surgery. Both preliminary and final eligibility confirmations will use the inclusion criteria in 4.1 and the exclusion criteria in 4.2.

6.1.3 Day Before Surgery (Day-1)

After admission, subjects will receive symptomatic treatment based on the underlying disease. Upon consent to surgery, relevant examinations will be completed on the day before surgery (Day –1), including:

- 1) Ophthalmic examinations: visual acuity (uncorrected and/or corrected), slit-lamp examination (anterior segment photography), intraocular

pressure measurement, corneal confocal microscopy, B-scan ultrasonography, and optical coherence tomography (OCT and/or panoramic OCT).

2) Concomitant medications.

6.1.4 Day of Surgery (Day 0)

1) On the morning of surgery, the subject's body temperature and blood pressure will be measured. If the subject's body temperature is $\geq 38^{\circ}$ C or hypertension (systolic blood pressure >200 mmHg, diastolic blood pressure >120 mmHg) is present, the surgery will be discontinued or postponed.

2) The subject will undergo ophthalmic examinations: slit-lamp examination (anterior segment photography) to confirm that the ocular conditions meet the surgical indications.

6.1.5 Postoperative day 1

Subjects will undergo ophthalmic examinations, including visual acuity assessment, slit-lamp examination (anterior segment photography), and intraocular pressure measurement.

6.1.6 Discharge Date

1) Subjects will undergo ophthalmic examinations including uncorrected and corrected visual acuity, slit-lamp microscopy (anterior segment photography), intraocular pressure, corneal OCT/panoramic OCT, corneal topography, and biomechanical assessment.

2) The investigator will record the subject's ocular status (inflammatory reaction, corneal epithelial healing time, hydrogel adherence) and the presence or absence of adverse events, with detailed documentation in the

electronic medical record.

6.2 Observation Period: Visits 1~4 (Week 1~Week 8)

6.2.1 Visits 1 (Week 1), Visits 2 (Week 2), 3 (Week 4), 4 (Week 8)

Within each visit window, the following assessments and evaluations will be performed:

- 1) The investigator will inquire about the subject's symptoms and signs since the last visit and the occurrence of any adverse events, with detailed documentation in the electronic medical record.
- 2) Subjects will undergo ophthalmic examinations including: visual acuity (uncorrected and/or corrected), slit-lamp examination (anterior segment photography), intraocular pressure measurement, corneal OCT + panoramic OCT (weeks 1, 4, and 8), B-scan ultrasonography (week 2), confocal microscopy (weeks 4 and 8), corneal topography (weeks 1 and 4), biomechanical assessment (weeks 1 and 4), and fundus photography (week 4).

6.3 Unscheduled Visits

During each study period, if the subject experiences discomfort or signs/symptoms outside the scheduled examination time, an unscheduled visit may be arranged as needed to conduct corresponding examinations and record them in a timely manner.

7. Examination/Observation Items

7.1 Subject Background

Data to be collected: sex, date of birth, date of informed consent, target disease (diagnosis, surgical eye), present illness, etiological diagnosis, comorbidities, past medical history, presence of drug allergy,

and concomitant medications.

7.2 Subjective symptoms of the surgical eye

Examination method: Record subjective symptoms of the surgical eye (e.g., discomfort, redness, photophobia, tearing, foreign body sensation) through subject interview.

7.3 Basic Examination

7.3.1 Visual Acuity Examination

Method: Measure the 5-meter visual acuity (uncorrected and corrected) of the eye.

7.3.2 Intraocular Pressure Examination

Method: Measure the IOP of the transplanted eye using a handheld tonometer or non-contact tonometer.

7.3.3 Corneal Shape Analysis

Method: Anterior segment OCT of the surgical eye to evaluate hydrogel adhesion and filling, as well as the thickness and corneal clarity of the repaired area.

7.3.4 Corneal Topography Examination

Method: Corneal topography was performed to measure the curvature and morphology of the surgical eye.

7.3.5 Biomechanical Assessment

Method: Biomechanical assessment was performed to measure the strength and toughness of the surgical eye.

7.3.6 Confocal Microscopy Examination

Method: Confocal microscopy was used to assess corneal endothelial cell density and morphology, as well as stromal cell migration and regeneration and nerve regeneration in the hydrogel-filled area.

7.4 Ophthalmological Findings

7.4.1 Conjunctival Findings

Method: Slit-lamp microscopy was used to assess conjunctival hyperemia and discharge of the surgical eye.

7.4.2 Corneal Findings

Method: Slit-lamp microscopy was used to observe corneal epithelial healing time, corneal clarity (degree of corneal opacity), corneal stromal inflammation, and infection of the surgical eye. Corneal opacity was clinically graded from 0 to 4 (0 = completely transparent; 1 = slight opacity, not easily detectable under direct illumination; 2 = mild opacity, visible on slit-lamp examination; 3 = moderate opacity, partially obscuring the iris; 4 = severe opacity, concealing intraocular structural details).

7.5 Clinical Examination Items

7.5.1 Hematological Examinations

Laboratory examination items

Examination Item	Examination Indicators
------------------	------------------------

Routine blood test	White Blood Cell count (WBC), Red Blood Cell count (RBC), Platelet count (PLT), neutrophil %, lymphocyte %, monocyte %, hemoglobin (HGB)
Urine routine	Urine occult blood, Urine pH, RBC count, WBC count, Urine glucose, Urine protein, Urine ketone bodies, Urine specific gravity
Blood biochemistry	
Liver function: Total bilirubin (TBIL), Direct bilirubin (DBIL), Indirect bilirubin (IBIL), Aspartate aminotransferase (AST), Alanine aminotransferase (ALT), Gamma-glutamyl transferase (GGT), Alkaline phosphatase (ALP), Total protein (TP), Albumin (ALB);
 
Renal function: Blood urea nitrogen (BUN), Creatinine (Cr);
 
Electrolytes: Calcium (Ca^{2+}), chloride (Cl^-), potassium (K^+), sodium (Na^+), magnesium (Mg^{2+});
 
Myocardial enzyme profile: Creatine kinase (CK), CK-MB, Lactate dehydrogenase (LDH)

Blood glucose	Fasting blood glucose, Glycated hemoglobin (HbA1c)
Coagulation function (four items)	Activated Partial Thromboplastin Time (APTT), International Normalized Ratio

	(INR), Prothrombin activity (PT%), Prothrombin Time Ratio (PT-R), Fibrinogen (FIB), Prothrombin Time (PT), Thrombin Time (TT)
Viral screening (four items)	Hepatitis B core antibody (HBcAb), Hepatitis B e antigen (HBeAg), Hepatitis B surface antigen (HBsAg), Hepatitis B e antibody (HBeAb), Hepatitis B surface antibody (HBsAb), HIV (1+2) antibody (HIV-Ab), Hepatitis C antibody (HCV-Ab), Treponema pallidum antibody (TP-Ab)

7.5.2 Other Preoperative Ophthalmic Examinations

Items: Electrocardiogram (ECG), Serological infection screening (Syphilis, HBV, HCV). If the subject has severe ocular surface inflammation, conjunctival sac culture will be performed simultaneously.

7.6 Adverse Events

Investigate adverse events through examinations during hospitalization and outpatient visits.

8. Fabrication of Sutureless Ophthalmic Hydrogel

8.1 Basic Overview of the Material

Name: Sutureless Ophthalmic Hydrogel

Components: decellularized porcine corneal stroma, methacrylated gelatin

8.2 Volume Specification

Container	Volume (Filled Volume)
Syringe	500 μ L

8.3 Fabrication of Sutureless Ophthalmic Hydrogel

8.3.1 Raw Material

Decellularized porcine corneal stroma, methacrylated gelatin (GelMA), recombinant human collagen.

8.3.2 Fabrication and Management of Sutureless Ophthalmic Hydrogel

8.3.2.1 Preparation of Decellularized Porcine Corneal Stroma Hydrogel (CECM)

- 1) Fresh porcine eyeballs were washed three times with sterile PBS in a laminar flow hood. After removing the epithelium with an epithelial scraper, central corneas were trephined using an 11 mm trephine. The endothelium was scraped off, and the corneas were soaked for 1 h in PBS containing penicillin–streptomycin.
- 2) Decellularization was performed by immersing the corneas in a solution containing 0.5% sodium lauroyl glutamate and 500 U/mL nuclease, with shaking at 120 rpm for 3 h at 37°C.
- 3) The corneas were washed six times with sterile PBS (15 min each), followed by two washes with sterile saline, and then freeze-dried.
- 4) To obtain the decellularized corneal stromal hydrogel (CECM), the samples were minced and soaked in 0.1 M HCl containing 10% pepsin for 18 h. The final concentration of the CECM solution was adjusted to 30 mg/mL, and it was stored at –20°C until use.

8.3.2.2 Preparation of Sutureless Ophthalmic Hydrogel

The sutureless ophthalmic hydrogel is formulated using methacrylated gelatin (GelMA) as the base matrix, which can be combined with biological materials such as decellularized porcine corneal stroma (CECM) and collagen. The specific protocol is as follows:

Scheme 1: CECM/GelMA composite system

The prepared 3% CECM solution was first adjusted to near-neutral pH with 1 M NaOH, then precisely calibrated to pH 7.4 with 500 mM Tris-HCl buffer (pH 7.4) to ensure a stable pH environment. The neutralized CECM solution, 10% GelMA, and 0.2% NAP were mixed in proportion and stirred with a magnetic stirrer for 30 min until a homogeneous and transparent mixture was obtained. The mixture was filtered through a sterile filter to remove potential impurities and microorganisms, then dispensed into 1 mL sterile syringes and stored at 4°C to prevent degradation.

Scheme 2: Decellularized porcine corneal stroma powder/GelMA composite system

The dried decellularized porcine corneal stroma powder was reconstituted with sterile saline to prepare a 3% powder solution, stirred thoroughly, and allowed to hydrate for 2 h to ensure complete dissolution. Then, 10% GelMA and 0.2% NAP were added to the neutralized powder

solution, and the mixture was stirred for 1 h to form a homogeneous composite precursor solution. After filtration through a sterile filter, the solution was dispensed into 1 mL sterile syringes and stored sealed at 4°C until use.

8.3.3 Sutureless Ophthalmic Hydrogel for Repairing Corneal Stromal Defects

On the day of surgery, whether a sutureless ophthalmic hydrogel can be used to repair the corneal stromal defect will be determined by the principal investigator and at least two conflict-free physicians, based on a comprehensive assessment of the subject's condition and the corneal stromal defect. Routine surgery will be performed, and the subject will first receive peribulbar block anesthesia. The surgical details (date of implantation, anesthesia method, presence of concomitant surgeries/procedures, operation time, diameter of hydrogel repair) and the presence of intraoperative complications will be recorded in the case report form.

8.4 Matters Concerning Ensuring the Safety of Trial Treatment

8.4.1 Expected benefits

Filling the stromal defect with the hydrogel is expected to restore corneal thickness, improve corneal clarity, and enhance visual acuity in the short term, while holding long-term promise for inhibiting corneal scar formation and promoting corneal stromal regeneration.

8.4.2 Expected harms

8.4.2.1 Hydrogel detachment or displacement

Judgment criteria: Hydrogel displacement or absence in the graft area observed on slit-lamp examination.

Management method: The principal investigator and physicians performing regenerative medicine will discuss the treatment plan during the observation period.

8.4.2.2 Infection

Judgment criteria: Presence of corneal infiltrate/ulcer, sharp increase of cells in the anterior chamber or hypopyon, ocular discharge, and conjunctival hyperemia.

Management method: The principal investigator and attending physician will immediately discuss the treatment plan. Surgical removal of the hydrogel and aggressive anti-infective therapy will be initiated. Corneal transplantation will be performed if necessary. Corneal smear and culture will be obtained to identify the causative pathogen.

9. Adverse Event Evaluation/Reporting

9.1 Definition of Adverse Events

An adverse event is any unfavorable or unintended sign, symptom, or disease that occurs in a subject, regardless of whether it is related to the sutureless hydrogel repair of corneal stromal wounds or other treatments.

Furthermore, in this clinical study, planned hospitalizations and examinations before study initiation, as well as hospitalizations specified in the clinical study protocol, are not considered adverse events.

Among adverse events, those meeting the following conditions are called serious adverse events:

Resulting in death (Fetal)

Life-threatening

Requiring therapeutic hospitalization or prolonging hospitalization

Resulting in persistent/significant disability/incapacity

Congenital anomaly/birth defect

Other serious events equivalent to the above

9.2 Adverse Events Evaluation

All adverse events observed from subject enrollment to the end of the study will be evaluated as described below. Clinically significant abnormal changes in laboratory values compared with preoperative levels will be reported as adverse events.

9.2.1 Onset Date of Adverse Events

Refers to the date when the adverse event is confirmed. However, for asymptomatic complications or incidental diseases, the date of diagnosis (the date on which the diagnostic examination was performed) is considered the onset date of the adverse event.

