3.4 Study Method Overview

This clinical study is a single-center, single-arm, open-label, single-dose trial evaluating the safety and efficacy (therapeutic effect) of a sutureless ophthalmic hydrogel for repairing corneal lamellar defects in patients with such defects.

The study consists of a screening period, an implantation period, and an observation period. After obtaining informed consent and completing registration, patients undergo screening examinations to confirm eligibility and absence of exclusion criteria. Surgery is performed under topical anesthesia. Following lesion debridement, the stromal bed is dried with a sponge, and a cotton pad is placed over the pupillary area to protect the fundus. The hydrogel, pre-liquefied in a 37°C water bath, is instilled into the lamellar defect using a sterile syringe, then irradiated with a 365 nm light source at an intensity of 18 mW/cm² for 30 seconds to achieve curing. A bandage contact lens may be applied after the procedure.

On postoperative day 1, gel integrity, thickness, and ocular surface inflammation are assessed using slit-lamp microscopy. During the 8-week observation period following gel injection, subjects are required to attend a total of four follow-up visits (Week 1, Week 2, Week 4, and Week 8). If any safety concerns arise from the trial results, necessary additional measures will be taken, and the specific ethics committee will be notified and must grant re-approval.

The safety of this clinical study will also be evaluated by the ethics committee. After completion of the first subject, the principal investigator may request an ethics

committee meeting based on the occurrence of serious adverse events or other relevant conditions, to seek advice on whether to continue the study or amend the clinical study protocol.

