9.2.5 Outcome Date of Adverse Events

Record the date of recovery, improvement, unrecovery, or death during or after treatment. In addition, if the outcome date cannot be accurately specified, record the date of confirming the outcome content.

9.2.6 Correlation between adverse events and trial procedures and sutureless hydrogel repair of corneal wounds

The correlation with trial procedures and sutureless hydrogel repair of corneal wounds will be determined according to the following four categories.

Definitely related: Clear temporal correlation (including the course after surgery) and evidence of confirmed correlation;

Probably related: Clear temporal correlation (including the course after surgery), and factors other than the trial treatment, such as the primary disease, comorbidities, concomitant medications, and concurrent treatments, can be basically excluded;

Possibly related: Clear temporal correlation (including the course after surgery), other factors such as the primary disease, comorbidities, concomitant medications, and concurrent treatments can also be presumed, but the possibility caused by the trial treatment cannot be excluded;

Unrelated: No temporal correlation. It can be presumed to be caused by other factors such as the primary disease, comorbidities, concomitant medications, and concurrent treatments.

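### Section 9.2.1 dates symptomatic adverse events from their confirmation, so recorded onset can be late, duration too short, and onset can even fall after recovery

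*Protocol*

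**What the plan says.** Section 9.2.1 of the Protocol gives the general rule for the onset date: "Refers to the date when the adverse event is confirmed". One exception follows: "However, for asymptomatic complications or incidental diseases, the date of diagnosis", meaning the day of the diagnostic examination, is used instead. No sentence refers to the first symptom or sign.

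Three other places bear on this rule:

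- **Section 6.2.1 (follow-up visits).** At each visit the investigator asks about "symptoms and signs since the last visit and the occurrence of any adverse events". Section 7.2 also records symptoms by interview. An earlier start date can therefore be known at the visit.
- **Section 9.2.5 (outcome date).** The date of recovery, improvement or other outcome is recorded. The date on which the outcome was confirmed is used only where the true date cannot be pinned down.
- **Section 9.2.6 (relatedness).** The three related categories all require a clear temporal link, and the fourth begins "Unrelated: No temporal correlation".

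Section 9.4 makes the onset date and the outcome date required entries on the case report form.

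**The concern.** The exception opens with a contrast, which suggests that a different kind of date was meant for symptomatic events. As drafted, both branches give a detection date: confirmation in one, diagnosis in the other. Neither records when a symptomatic event began.

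The two ends of one event then follow opposite conventions, with onset taken at detection and outcome taken at its true date where known. Durations calculated from these fields are biased downwards, and some will be impossible.

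Safety is the primary objective (Section 2.1). The study has one arm and one application of the hydrogel, so there is no control group against which to judge excess events, and time since implantation is one of the main guides to attribution. Section 10.1 counts events caused by the hydrogel and by the procedure as secondary safety items, and its overall safety grade depends on study-related effects. A reliable onset date is therefore worth having. If it is not collected at the visit, it may not be recoverable later.

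**Working it through.** The protocol gives no figure for error in onset dates, so there is nothing to reproduce. The check is arithmetic on the visit schedule plus a comparison of the two dating rules.

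**Inputs.** Surgery is Day 0 (Section 6.1.4). There is a postoperative check on Day 1 (Sections 3.4 and 6.1.5). Visits follow at Weeks 1, 2, 4 and 8 (Sections 3.4 and 6.2.1), that is Days 7, 14, 28 and 56. The discharge examination (Section 6.1.6) has no fixed day and is left out; it could only shorten a gap.

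**Step 1: largest delay.** If an event is confirmed at the next scheduled contact, the largest delay equals the gap between contacts.

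| Interval | Largest delay (days) | Mean delay if onset is uniform (days) |
|---|---|---|
| Day 0 to 1 | 1 | 0.5 |
| Day 1 to 7 | 6 | 3 |
| Day 7 to 14 | 7 | 3.5 |
| Day 14 to 28 | 14 | 7 |
| Day 28 to 56 | 28 | 14 |

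The longest gap is 56 − 28 = 28 days, which is 28/56 = half of follow-up.

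**Step 2: mean delay over follow-up.** This assumes uniform onset over Days 0 to 56 and confirmation only at these contacts. Mean delay = Σ(gap²)/(2 × 56) = (1 + 36 + 49 + 196 + 784)/112 = 1066/112 ≈ 9.5 days. The protocol does not support uniform onset. If postoperative events cluster early, the mean is smaller, since no gap before Week 2 exceeds 7 days.

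**Step 3: visit windows.** Section 6.2.1 mentions a window around each visit without a width. With an assumed window of ±w days, the longest gap is 28 + 2w: 28, 34 or 42 days for w = 0, 3 or 7.

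**Step 4: the two rules applied to one event.**

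- *Resolved before the visit.* A symptom starts on Day 30, resolves on Day 40, and is first reported and confirmed at Week 8. Section 9.2.5 gives an outcome date of Day 40. Section 9.2.1 gives an onset date of Day 56. True duration is 40 − 30 = 10 days; recorded duration is 40 − 56 = −16 days.
- *Still present at the visit.* A symptom starts on Day 16, is confirmed at Week 4 (Day 28) and resolves on Day 35. True duration is 35 − 16 = 19 days; recorded duration is 35 − 28 = 7 days.

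The first case needs no unusual behaviour: a mild symptom that passes before the visit and is picked up by the history question is enough.

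**The case against.** The strongest reply is that little in the planned evaluation depends on this date. The primary safety assessment concerns which events occur, how severe they are and how often, and the protocol describes no time-to-onset analysis. Several named events are found by examination (hydrogel detachment, endothelial change, raised pressure); where these are silent, the diagnosis date is reasonable. The word confirmed is undefined and could be read loosely. Section 6.3 allows an unscheduled visit for symptoms between visits, so a four-week delay needs a symptomatic subject who makes no contact. All of this stands and limits the size of the point. The loose reading is hard to sustain beside Section 9.2.5, which shows that the protocol can separate a true date from a confirming date when it means to.

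Three stronger readings are tempting, and the document does not support them:

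- **That late dating turns related events into unrelated ones.** Section 9.2.6 sets no time window and does not cite the Section 9.2.1 date. The investigator has the symptom history when judging relatedness, and a postoperative event dated late still follows the implant.
- **That events move between visits in the Section 11.3 summaries.** An event confirmed at the next visit stays in the same visit interval under either dating, and Section 11.3 does not mention onset date.
- **That complaints from before surgery become postoperative events.** The Day −1 ophthalmic examination (Section 6.1.3) and the Day 0 slit-lamp check (Section 6.1.4) largely guard against this, and Section 9.2 evaluates events from enrolment onwards.

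**Conclusion.** The point holds as a defect in a recording rule. Section 9.2.1, followed as written, gives wrong onset dates for symptomatic events and conflicts with the convention in Section 9.2.5. Onset can be up to 28 days late on the nominal schedule. That is a worst case, for an event starting just after Week 4, confirmed at Week 8, with no unscheduled contact. Recorded duration is shortened, and an event that starts and resolves between visits can carry an onset after its recovery.

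The recorded date is a poor input to the timing judgment in Section 9.2.6, but that effect is qualitative and cannot be sized from the protocol. Counts and severity of events are unaffected. The correction is worth making before enrolment because safety is the primary objective and the design has no control group.

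**What to change.** Reword Section 9.2.1 so that onset is the date of the first symptom or sign, as reported by the subject or recorded, whichever is earlier. Use the confirmation date only when that date cannot be specified, mirroring Section 9.2.5. Keep the diagnosis date for asymptomatic findings. Add a separate case report form field for the confirmation date, so that the delay between onset and detection can be seen.

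The cost is about one sentence and one field. The history needed is already taken at every visit, and no sample size, visit or treatment rule changes. The small downside is recall error in dates given by subjects; the separate confirmation date bounds it, since a subject's reported start cannot be later than confirmation.
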